## **Statistical Analyses**

### **Primary Endpoints**

Safety and toxicity

a. DLT Rate

Proportion of patients who developed a DLT as a result of NeoVax therapy.

### **Secondary Endpoints**

a. Best Response to Therapy

The number of patients with best response of CR or PR (per RECIST 1.1) will be summarized. For rate estimation, the denominator is the number of patients in each cohort.

b. Disease Progression/Recurrence

The number of patients with disease progression (unresectable) or disease recurrence (resectable).

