3.1.1 Inclusion Criteria

3.1.1.1 Participant is willing and able to give written informed consent

3.1.1.2 Participants must have histologically confirmed stage IIIB/C/D or stage IV cutaneous melanoma (mucosal melanoma or uveal melanoma are excluded) that is surgically resected, is deemed surgically resectable, or is unresectable; tumor tissue for sequence analysis must be available from either previous melanoma resection/biopsy or at least one site of disease must be amenable to surgical or core biopsy

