4. REGISTRATION PROCEDURES

Eligibility will be confirmed prior to the initial biopsy to obtain tumor for sequencing. Prior to initial biopsy, the patient is screened for eligibility using the eligibility checklist. Once overall trial initial eligibility is confirmed, the patient is registered, undergoes core needle or surgical biopsy and preparation of the participant's vaccine is initiated (while the patient is receiving Nivolumab).

Before the first dose of the vaccine plus ipilimumab the patient will be registered to the correspondent dose level vaccine plus ipilimumab.

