5.2.1.3 Nivolumab Continuation Period

After neoantigen vaccine (NeoVax plus Montanide) / Ipilimumab treatment has been completed, patients with unresectable stage IIIB/C/D or IV melanoma will continue to receive Nivolumab alone at a flat dose of 480 mg as a 30 minutes (+/- 10 min.) i.v. infusion every 4 weeks (28 days), until disease recurrence or progression, unacceptable toxicity, or withdrawal of consent, for a maximum duration of up to 2 years from the first study treatment in the Run in Period. Participants with completely resected melanoma will receive nivolumab for a maximum period of one year (13 doses)

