5.4.3 Definition of evaluable participants

All participants receiving at least one dose of Nivolumab will be evaluable for toxicity. Participants will be evaluable for immunologic activity if they have received all vaccinations during the priming phase and the first boost vaccination.

Participants with unresectable and measurable disease who have received at least one dose of study vaccine therapy will be considered evaluable for determination of tumor response.

A minimum of 2 vaccinations and absence of DLTs are required for a participant to complete the

6-week DLT observation period successfully.

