11.1.1 Definitions

Evaluable for Target Disease response. Only those participants who have measurable disease present at baseline, have received at least one cycle of therapy, and have had their disease re-evaluated will be considered evaluable for target disease response. These participants will have their response classified according to the definitions stated below. (Note: Participants who exhibit objective disease progression prior to the end of cycle 1 will also be considered evaluable.)

Evaluable Non-Target Disease Response. Participants who have lesions present at baseline that are evaluable but do not meet the definitions of measurable disease, have received at least one cycle of therapy, and have had their disease re-evaluated will be considered evaluable for non-target disease. The response assessment is based on the presence, absence, or unequivocal progression of the lesions.

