11.1.4 Response Criteria

11.1.4.1 Evaluation of Target Lesions

Complete Response (CR): Disappearance of all target lesions. Any pathological lymph nodes (whether target or non-target) must have reduction in short axis to <10 mm.

Partial Response (PR): At least a 30% decrease in the sum of the diameters of target lesions, taking as reference the baseline sum diameters.

Progressive Disease (PD): At least a 20% increase in the sum of the diameters of target lesions, taking as reference the smallest sum on study (this includes the baseline sum if that is the smallest on study). In addition to the relative increase of 20%, the sum must also demonstrate an absolute increase of at least 5 mm. (Note: the appearance of one or more new lesions is also considered progressions).

Stable Disease (SD): Neither sufficient shrinkage to qualify for PR nor sufficient increase to qualify for PD, taking as reference the smallest sum diameters while on study.

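### The SAP's CR/PR rate divides by every patient in the dose cohort, including completely resected patients, whom the protocol's response-evaluable set leaves out

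*SAP*

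**What the plan says.** SAP, Statistical Analyses, Secondary Endpoints, item a, summarizes the number of patients with a best response of CR or PR per RECIST 1.1 and adds: "For rate estimation, the denominator is the number of patients in each cohort". The SAP's Design section uses the word cohort for groups that differ in ipilimumab dose, planned at five patients each. Its Modified Design paragraph says the expansion cohort never began.

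Protocol 5.4.3 sets a narrower population for response: "Participants with unresectable and measurable disease who have received at least one dose of study vaccine therapy will be considered evaluable". The same section uses a wider one for safety: "All participants receiving at least one dose of Nivolumab will be evaluable for toxicity". Protocol 11.1.1 words response evaluability differently ("Only those participants who have measurable disease present at baseline, have received at least one cycle of therapy", plus a re-evaluation). Its parallel definition for non-target disease also needs lesions at baseline.

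Protocol 3.1.1.2 admits melanoma "that is surgically resected, is deemed surgically resectable, or is unresectable". Section 5.2.1.3 gives completely resected patients their own nivolumab duration, so they are treated on study in the same dose cohorts.

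**The concern.** RECIST response is a change in disease that is present at baseline. Partial response, for example, is "At least a 30% decrease in the sum of the diameters of target lesions, taking as reference the baseline sum diameters". A completely resected patient has no baseline sum and no lesion to disappear, so CR or PR cannot be recorded. Under the SAP sentence that patient still counts in the denominator.

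The SAP rate therefore mixes two things: how often patients with disease respond, and how many patients in the cohort had disease at all. Cohorts with different shares of resected patients would show different rates for the same activity, or the same rate for different activity. The SAP separates unresectable from resectable patients for progression and recurrence (endpoint b), and protocol 13.1 makes a similar split. Response (endpoint a) has no such split, and the SAP gives no reason for leaving the 5.4.3 set.

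**Working it through.** **Inputs.**
- Cohort size n = 5 (SAP Design; protocol 5.4.1 and 13.1).
- Neither document states a response rate or a sample size based on response, so there is no plan figure for response to reproduce. The cohort size can be checked against the plan's dose-expansion table: P(0 or 1 DLT in 5) = (1−p)^5 + 5p(1−p)^4. At p = 0.10 this is 0.590 + 0.328 = 0.919. At p = 0.20 to 0.60 in steps of 0.10 it is 73.7, 52.8, 33.7, 18.8 and 8.7%. The plan states 92, 74, 53, 34, 19 and 9%, so n = 5 is consistent.
- The number completely resected, r, is not given. It is varied from 0 to 4.

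**Formulas.** Let e be the patients in the 5.4.3 set, x the responders among them, and y the responders outside the set.
- SAP rate = (x+y)/n. Rate on the 5.4.3 set = x/e.
- (x+y)/n < x/e ⇔ e(x+y) < nx ⇔ ey < (n−e)x ⇔ y/(n−e) < x/e, for e < n.
- With y = 0, x ≥ 1 and e < n this always holds, and the SAP rate equals the 5.4.3 rate times e/n. If everyone not resected is evaluable, e = 5−r and the factor is (5−r)/5.

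**Results with n = 5, y = 0 and all non-resected patients evaluable.**

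| r | Factor | One responder: SAP vs 5.4.3 | Two responders: SAP vs 5.4.3 |
|---|---|---|---|
| 0 | 1.0 | 1/5 = 20% vs 1/5 = 20% | 2/5 = 40% vs 2/5 = 40% |
| 1 | 0.8 | 20% vs 1/4 = 25% | 40% vs 2/4 = 50% |
| 2 | 0.6 | 20% vs 1/3 = 33% | 40% vs 2/3 = 67% |
| 3 | 0.4 | 20% vs 1/2 = 50% | 40% vs 2/2 = 100% |
| 4 | 0.2 | 20% vs 1/1 = 100% | not possible |

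A 5.4.3 rate of 50% appears as 40% when r = 1 and as 20% when r = 3. Rates of 25% (1/4) and 50% (1/2) both appear as 20%.

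**All combinations.** With r ≥ 1, x ≥ 1 and y = 0 there are e(5−e) combinations for each e: 4 + 6 + 6 + 4 = 20. All give a lower SAP rate.

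**Where the direction changes.** Protocol 11.1.4.4 allows CR in patients with only non-measurable disease, who are outside the 5.4.3 set.
- With r ≥ 1, x ≥ 1 and y ≥ 1, exactly two combinations reverse the order. First: one resected, three evaluable with one responder, one other patient who responds, giving 2/5 = 40% vs 1/3 = 33%. Second: one resected, two evaluable with one responder, two others who both respond, giving 3/5 = 60% vs 1/2 = 50%.
- With x = 0 it can also reverse: one resected, three evaluable non-responders and one other responder give 1/5 = 20% vs 0/3 = 0%.
- With no responders both rates are 0%. With e = 0 the 5.4.3 rate is undefined.

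**The case against.** **An all-patient denominator can be a deliberate, conservative choice, and the SAP states it openly.** Counting everyone guards against dropping patients for what happens after treatment starts. Complete resection is known at baseline, so leaving these patients out does not select on outcome. The SAP does not claim conservatism or mention 5.4.3. What stands is that the all-patient proportion is worth keeping beside the other.

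**The practical effect is small.** This largely stands. The CR/PR count is reported in any case, response is not among the protocol's secondary endpoints in 13.1, and no comparison between cohorts is planned in the SAP text available. At these sizes the uncertainty is larger than the differences: 90% exact intervals are 1.0–65.7% for 1/5, 1.3–75.1% for 1/4 and 2.5–97.5% for 1/2.

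**The 5.4.3 set is not perfect either.** This also stands. It leaves out patients with only non-measurable disease, and patients whose disease was judged resectable but was not resected; either group could respond. The section also refers to a priming phase and a first boost, which do not appear in the four-dose schedule of 5.2. It is still the protocol's own set for response. Unlike 11.1.1 it needs no re-evaluation scan, so a vaccinated patient who leaves before the next scan stays in as a non-responder.

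**The vaccine-dose condition could remove further patients.** Probably few. Protocol section 4 says: "Before the first dose of the vaccine plus ipilimumab the patient will be registered to the correspondent dose level vaccine plus ipilimumab". Patients lost during the nivolumab run-in would therefore probably have no dose cohort under the SAP either.

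**A stronger reading.** A reader might infer that the SAP always understates the response rate. The documents do not support this, because the direction depends on the conditions set out in the working.

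**Conclusion.** The point holds in a limited form. The SAP sentence conflicts with protocol 5.4.3 and gives a rate that depends on case mix. The SAP rate is certain to be too low, relative to the 5.4.3 rate, when a cohort has at least one evaluable responder, at least one completely resected patient and no responder outside the set. For a cohort of 5 with everyone else evaluable, the reduction is 20% to 80% in relative terms for r = 1 to 4, and nil for r = 0.

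This rests on the planned cohort size and an assumed range for r. The documents give neither the number resected nor the number of responders. A reader might conclude that a reported result is wrong, or that the safety findings are touched. Neither follows: no distorted result is shown, and the DLT rate, the MTD and the CR/PR count do not use this denominator. It is a minor-to-moderate correction to a descriptive endpoint, and it should be made.

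**What to change.** Replace the SAP's denominator sentence with wording such as:

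> The response rate in each dose cohort is calculated among patients evaluable for tumor response under protocol 5.4.3; completely resected patients are not included. The number evaluable is shown beside the cohort total, and the proportion of all patients in the cohort is given as a supplementary figure. Any CR or PR in a patient with baseline disease outside the 5.4.3 set (non-measurable, or resectable but not resected) is listed separately.

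Take disease status from baseline records and vaccine exposure from dosing records. The change applies to the response rate only. Completely resected patients stay in the toxicity, DLT and immune analyses under the rules that govern those.

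**Cost.** One SAP passage and one baseline disease-status flag. AJCC stage, listed under the SAP's Disease Characteristics, cannot serve as that flag, because stage IIIB/C/D or IV disease may be resected or unresectable. Part of the SAP text was not available to us, so a suitable flag may already exist. The drawback is smaller denominators and wider intervals, which the cohort total and the supplementary proportion put in context.

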1.3 Secondary Objective

- To assess the induction of neoantigen-specific cellular immune responses following administration of NeoVax plus Montanide in combination with Nivolumab and locally administered Ipilimumab
- To estimate rates of disease progression/recurrence depending on whether the patient had all melanoma resected or has measurable disease per RECIST 1.1

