5.7 Duration of Therapy / Criteria for Taking a Participant Off Protocol Therapy

Duration of therapy will depend on tolerability of the immunizations and evidence of disease recurrence or progression as judged by the treating investigator. In the absence of treatment delays due to adverse events, treatment will be given for two years in patients with unresectable melanoma and for one year (13 doses) for participants with stage III/B/C/D or IV completely resected melanoma, respectively, or until one of the following criteria applies:

- Disease progression or recurrence, if it is deemed by the treating investigator to be in the best interest of the participant to discontinue study treatment. If there is clinical or radiographic disease progression or recurrence prior to initiation of vaccine at week 12 or at the week 12 scan, treatment as per protocol (Nivolumab plus NeoVax + Montanide + local Ipilimumab) should be given unless deemed not in the best interest of the patient by the investigator.
- Intercurrent illness that prevents further administration of treatment
- Unacceptable adverse event(s)
- Participant demonstrates an inability or unwillingness to comply with protocol requirements
- Participant decides to withdraw from the study, or
- General or specific changes in the participant's condition which render the participant unacceptable for further treatment in the opinion of the treating investigator.

Participants will be removed from the protocol therapy when any of these criteria apply. The reason for removal from protocol therapy, and the date the participant was removed, must be documented in the case report form (CRF). Alternative care options will be discussed with the participant.

When a participant is removed from protocol therapy and/or is off of the study, the relevant Off-Treatment/Off-Study information will be updated in OnCore.

In the event of unusual or life-threatening complications, participating investigators must immediately notify the Principal Investigator, [name], PhD at DFCI [REDACTED]

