11. MEASUREMENT OF EFFECT

Although response is not the primary endpoint of this trial, participants with measurable disease will be assessed by standard criteria. For the purposes of this study, participants should be re-evaluated every 12 weeks. In addition to a baseline scan, confirmatory scans will also be obtained 4 weeks following initial documentation of an objective response.

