11.1 Antitumor Effect – Solid Tumors

For the purposes of this study, participants should be re-evaluated for response every 8 weeks. In addition to a baseline scan, confirmatory scans should also be obtained 4 weeks following initial documentation of objective response.

Response and progression will be evaluated in this study using the new international criteria proposed by the Response Evaluation Criteria in Solid Tumors (RECIST) guideline (version 1.1) [Eur J Ca 45:228-247, 2009]. Changes in the largest diameter (unidimensional measurement) of the tumor lesions and the shortest diameter in the case of malignant lymph nodes are used in the RECIST criteria.

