Timelines: We expect to enroll one patient per month. We expect FPFV to occur by September 2020. LPFV is expected for July 2022 and overall duration of the study will be 4 years.

Analysis of Secondary Endpoints

Secondary endpoint in this clinical trial will: (a) assess the induction of IFN- γ T-cell response or tetramer staining to the assay peptides, and (b) to estimate rates of disease progression or recurrence (RECIST 1.1) depending on whether the patient is resected or has measurable disease. Analyses of the secondary endpoint will be based on 15 patients treated at the MTD.

The induction of IFN- γ T-cell response will be based on ELISPOT assessments taken prior to vaccine administration and at week 16. The proportion of patients who achieve more than 55 SFU/10⁶ PBMC or 3 times their baseline level will be presented with a 90% exact binomial

confidence interval. Based on a cohort of size 15, the confidence interval will be no wider than 0.46.

The proportions of patients with disease progression or recurrence, according to melanoma stage, will be presented with 90% exact binomial confidence intervals.

Analysis of Correlative Endpoints

Longitudinal analyses of PBMC immune response kinetics to the peptide pool and to individual epitopes will be presented graphically and descriptively at each time point. Changes in the magnitude of the response relative to pre-treatment at several different time points after vaccination will be summarized descriptively. Changes in response between pre-treatment and 16 weeks post-vaccination, which is the time of the primary immunologic endpoint, will be assessed using the Wilcoxon signed-rank test.

Immune studies of T cell subpopulations (CD4⁺, CD8⁺, central/effector memory cells, Th1/Th2 cells, T-reg, etc.), myeloid-derived suppressor cells (MDSC), CTL response, and T cell activation status will be summarized using descriptive statistics.

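### Progression/recurrence is to be estimated as a rate by resected versus measurable disease, but the SAP gives a count with no time point, denominator or censoring, and the protocol's analysis sentence groups by stage

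*SAP*

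**What the plan says.** Protocol 1.3 sets the objective: "To estimate rates of disease progression/recurrence depending on whether the patient had all melanoma resected or has measurable disease per RECIST 1.1". The endpoint sentence in Protocol 13.1 keeps that grouping: "rates of disease progression or recurrence (RECIST 1.1) depending on whether the patient is resected or has measurable disease".

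The analysis sentence later in Protocol 13.1 does not: "The proportions of patients with disease progression or recurrence, according to melanoma stage, will be presented with 90% exact binomial confidence intervals". It names no time point. Section 13.1 bases the secondary analyses on 15 patients treated at the MTD.

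The SAP's analysis entry, under Statistical Analyses, Secondary Endpoints, item b, is "The number of patients with disease progression (unresectable) or disease recurrence (resectable". Its endpoint definition says the same in slightly more words. The one denominator given there, patients in each cohort, belongs to item a, best response. The protocol's 90% interval does not appear.

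Protocol 11.1.6 defines PFS and time to progression from registration, with censoring at the last disease evaluation. Protocol 5.9 says which progression date counts for patients treated beyond progression. SAP data sections 5 (Deaths and Overall Survival) and 6 (Time to Progression) list death, last-follow-up and progression dates. Neither Protocol 13.1 nor the SAP's Statistical Analyses links any of this to an analysis.

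**The concern.** A count of events is a rate only once one knows how many patients were observed and for how long. Here observation time will differ between patients. Protocol 13.1 expects one patient a month, with first visits from September 2020 to July 2022. Protocol 5.10 takes patients off study for loss to follow-up, withdrawal, a DLT, a severe skin ulcer or failed vaccine production, none of which requires progression. A crude count leaves such patients in as event-free, and it rises with a later data cut.

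The grouping matters as well. Recurrence after complete resection and progression of measurable disease are different outcomes with different expected frequencies. A table by stage would mix them. The result would be a figure that does not answer the stated objective and that readers cannot place in time.

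**Working it through.** **1. Grouping, side by side.**

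- Protocol 1.3: split "depending on whether the patient had all melanoma resected or has measurable disease per RECIST 1.1".
- Protocol 13.1, endpoint sentence: resected versus measurable.
- Protocol 13.1, analysis sentence: melanoma stage.
- SAP: resectable versus unresectable.

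Protocol 3.1.1.2 admits stage IIIB/C/D or IV disease that is resected, resectable or unresectable, so stage does not determine resection status. The SAP's labels are closer to the objective but not identical. Under Protocol 11.1.2 disease can be non-measurable, and an unresectable patient with only such disease fits neither group in the objective.

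**2. The plan's own precision figure.** Protocol 13.1 states a maximum width of 0.46 for a 90% exact interval with 15 patients. It is stated for the ELISPOT proportion, but the progression proportions use the same method. The Clopper-Pearson limits are

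lower = Beta⁻¹(0.05; x, n−x+1), upper = Beta⁻¹(0.95; x+1, n−x).

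The widest case at n = 15 is x = 8: 0.300 to 0.756, width 0.456. The stated figure reproduces.

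**3. Precision after the design change.** The SAP reports that the expansion cohort never opened. The number treated is not stated. If both escalation cohorts filled, it is 5 + 5 = 10 (assumption), of whom 15 − 10 = 5 would be at the MTD. Maximum 90% widths by the same formula:

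| Group size | Maximum width |
|---|---|
| 10 | 0.56 |
| 7 | 0.65 |
| 5 | 0.73 |
| 3 | 0.85 |

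A 5/5 split by disease setting gives 0.73 in each group; a 7/3 split gives 0.65 and 0.85. In a group of five, reclassifying one patient moves the proportion by 1/5 = 0.20.

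**4. Effect of leaving out the time point.** Protocol 2.3.5.4 cites recurrence-free survival on adjuvant nivolumab of 70.5% at 12 months and 58% at 3 years.

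- Event proportion at 12 months: 1 − 0.705 = 0.295.
- Event proportion at 36 months: 1 − 0.58 = 0.42.
- Difference: 0.42 − 0.295 = 0.125.

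The same patients under the same treatment give proportions 12.5 points apart, depending only on when they are counted. On the planned dates, the first and last patients entered 22 months apart (September 2020 to July 2022), so a single data cut would see them at quite different times.

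**The case against.** The strongest reply is that this is a descriptive secondary endpoint in a very small single-arm trial. With perhaps five patients per group, a Kaplan-Meier landmark adds little to a list of each patient's event and follow-up times. The protocol already holds censored definitions, and the SAP lists dates. This stands in part. It limits how much the point matters and is a reason to show individual times. It does not justify a count with neither denominator nor follow-up.

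Some stronger readings are tempting, but the documents do not support them:

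- *Active follow-up stops at new therapy, so progressions are missed.* Protocol 5.8 ends it at new therapy for progressive disease, which comes after the event. The possible losses come from withdrawal and the exits in Protocol 5.10.
- *The SAP analyses by stage.* It does not; the stage wording is in one sentence of Protocol 13.1.
- *Run-in progressions are counted against the combination.* Protocol 5.7 covers progression "prior to initiation of vaccine at week 12 or at the week 12 scan" and says protocol treatment should generally still be given. Such events would enter the count, but neither document attributes them to any component.
- *The scan-interval conflict distorts the count.* Protocol 11.1 says "participants should be re-evaluated for response every 8 weeks"; Section 11 says "participants should be re-evaluated every 12 weeks", and the Study Calendar agrees with Section 11 after week 24. A crude count uses no event times, so the conflict matters only once times are analysed.
- *The results were meant to be compared with the cited nivolumab trial.* Protocol 13.1 plans no such comparison.
- *The cited curve yields an expected range for this trial.* No data cut-off is given, the entry dates are planned ones, the SAP reports slow accrual, and the curve covers resected patients only.

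**Conclusion.** The point holds. The SAP's count does not estimate the rate named in the objective: it lacks a denominator, time horizon, interval and censoring rule, and it drops the protocol's 90% interval. Protocol 13.1 has the interval but no time point, and its stage grouping contradicts its own endpoint sentence.

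The size of any distortion in this trial cannot be computed, because the number treated, the split by disease setting, actual follow-up and the data cut-off are not stated. The 12.5-point difference shows only that time matters. The interval widths assume ten patients. The change is worth making because the definitions and most of the needed dates already exist. The primary DLT endpoint and its operating characteristics are not touched.

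**What to change.** - **Link the analysis to the definitions.** Tie SAP item b to Protocol 11.1.6. Report Kaplan-Meier PFS for unresectable/measurable disease, and recurrence-free survival (the same definition with recurrence in place of progression) for resected disease. Use a stated landmark such as 12 months, with 90% confidence intervals.
- **State the time origin.** Measure from registration. Protocol 3.1 has an initial and a secondary registration, so name which.
- **State the data.** Give the data cut-off, denominators, follow-up duration and each patient's event or censoring time. Say how deaths without progression are handled. Keep the counts as supportive. Confirm that the date of last disease evaluation is extracted, since a last-follow-up date is not the same thing.
- **Use one grouping.** In Protocol 13.1 replace the stage wording with resected versus measurable, use the same labels in the SAP, and say where unresectable non-measurable disease goes.
- **Flag early events.** Mark descriptively any event before first vaccination.
- **Reconcile the scan interval.** Protocol 11.1 conflicts with Section 11 and the Study Calendar, and this will affect progression dates once they are analysed.

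The cost is some wording, one standard analysis and one listing. The intervals will be very wide, and the report should say so.
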